Under the direction of [name], the Severe Behavior Unit at the Marcus Autism Center has extensive experience in the application of specialized behavioral assessment and treatment of SIB in children with ASD. This work, based on the principles of applied behavior analysis, considers the purpose or *function* of SIB when selecting treatment components for a child. Through the careful analysis of function (see below), we classify SIB that is reinforced by social reward such as allowing escape from a routine demand, or obtaining a preferred object (a food or a toy) or gaining caregiver attention. Alternatively, we classify SIB as a repetitive, *automatic* behavior that is somehow self-reinforcing. The techniques of applied behavior analysis are predictably more successful for reducing SIB maintained by *social* reward than *automatically* maintained SIB. This observation suggests that neural pathways that underlie habitual *automatically* maintained SIB may be different from those underlying socially maintained SIB. This study is focused on automatically maintained SIB.

Aim #1. To demonstrate the feasibility of conducting a 9-week, randomized, double-blind trial of NAC compared to placebo in 14 children (age \geq 5- \leq 12 years 11 months) with ASD and moderate level of SIB

Feasibility includes demonstrating successful recruitment of eligible subjects for a randomized, placebo-controlled study of NAC, that the treatment is acceptable to parents, and successful collection of study outcome measures. **Benchmarks include:**

- a) demonstrate capacity to screen 2-3 subjects/month (in order to average 1.75 randomize subjects/month);
- b) no more than 15% attrition rate (e.g., no more than 2 of 14 randomized subjects);
- c) at least 70% compliance with study medication (determined by tablet counts and drug dairies).
- d) at least 80% collection of essential outcome measures (actual ratings \div expected \times 100).
- e) at least 80% of parents will *agree* or *strongly agree* when asked in an anonymous survey that they would recommend the study and the study treatment to other parents of children with ASD and SIB.

Aim #2. To evaluate the positive predictive value of our screening method to classify children with automatically maintained self-injurious behavior.

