The definitive method of classifying SIB as *socially* maintained or *automatically* maintained is a specialized five- to six-hour assessment called a *functional analysis*. We intend to enrich the study sample with children classified with automatically maintained SIB based on the functional analysis. To minimize subject burden and to manage study resources, we want to avoid conducting the detailed functional analysis on subjects who do not get classified with automatically maintained SIB. We have developed a screening interview to aide in identification of subjects with automatically maintained SIB before undertaking the detailed functional analysis. Demonstrating a high positive predictive value is a necessary prerequisite for launching a larger study. Using the formula: Positive Predictive Value (PPV) = screen positive and true cases \div all positive screens, we set a benchmark of 75%. Information learned in the study will likely enhance our PPV for future studies.

NOTE: Children who are classified with socially maintained SIB will not be randomized. [name] will meet with the family to plan the next phase of treatment.

Aim #3. To evaluate the preliminary efficacy of NAC for reducing SIB in 14 children with ASD in a 9-week, double-blind, placebo-controlled, randomized trial.

This sample size is not sufficient to test the superiority of NAC over placebo. We use a randomized design to meet Aim #1 and to enable blinded assessment of outcome by an independent evaluator.

Preliminary efficacy benchmarks within the NAC group

- a) Significant decline from baseline to Week 9 on the parent-rated Aberrant Behavior Checklist Irritability subscale (commonly used parent-rated survey of tantrums, aggression, and self-injury).
- b) at least 50% decline (on average) from baseline to Week 9 in the number of SIB events in children treated with NAC when counted by a trained technician who is blind to treatment assignment.

c) at least 50% of the subjects on will be rated *much improved* or *very much improved* on the Improvement scale of the Clinical Global Impression by a clinician blind to treatment assignment.

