Pilot studies are not about efficacy (Leon et al., 2011). Before launching a larger **definitive** randomized clinical trial, we need to show that the study procedures and medication are acceptable to parents, that we can successfully recruit and retain children with moderate to severe repetitive SIB in a randomized trial, and that we can collect outcome data. Fourteen children with ASD will be enrolled and randomly assigned to NAC or placebo for 9 weeks. Enrollment will occur from Month 2 through Month 9 of the project (average at least 1.75 subjects per month). Children will be recruited through the Marcus Autism Center (from the current waitlist and referrals). Potentially eligible children will be screened by phone to confirm the presence of SIB that is moderate – but not in need of immediate service. Children with presumably moderate SIB will be invited to come to Marcus for a formal screening visit to confirm eligibility (see Table 2 for Schedule of Measures).

Table 2.0 – Schedule of Measures

Measures	Staff	Screen	FA Screen	Baseline	Study Week				
					1	2	4	6	9
ABC	RC	X		X			X		X
Adverse Event	MD	X		X	X	X	X	X	X
CGI-I	IE			X			X		X
CGI-S	IE	X		X			X		X
CGSQ	RC			X			X		X
Cognitive Test (Mullen or Stanford-Binet 5)	IE	X							
CYBOCS-ASD	IE			X			X		X
Demographic Form	RC	X							
Detailed Functional Analysis	IE/RC		X						X
Direct Observation Session	IE/RC			X					X
Drug Compliance	RC				X	X	X	X	X
DSM-V checklist	IE	X							
Functional Assessment Interview	IE	X							
Medical History	IE	X							
Parent Satisfaction Questionnaire	RC								X
Parent Target Problem	IE	X		X			X		X
Physical Exam	MD	X							
Research lab test**	RC	X							X
Responder Status	IE								X
Routine blood tests*	RC	X							X
Safety Review	MD	X		X	X	X	X	X	X
SCQ	RC	X							
Treatment Review and Planning	Clinic								X
Vineland III	RC	X							
Vitals, Height and Weight	RC	X		X			X		X

* CBC, electrolytes, BUN, creatinine, liver function tests

** see Aim 5 (drawn at same time points of safety labs)

Subject Characterization Subjects will be characterized in accordance with current practice at Marcus to confirm an ASD diagnosis and essential clinical characteristics (e.g., IQ, adaptive functioning, behavioral problem profile). For details, see Appendix A.

Inclusion criteria

1. Boys and girls ≥ 5 and ≤ 12 years 11 months
2. Confirmed diagnosis of ASD (clinical interview, Social Communication Questionnaire, DSM-V checklist)

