3. Medication- free or stable medication (at least four weeks) with no planned changes for the 9-week trial.
4. Anticonvulsants for seizures will be allowed if the dosage has been stable for 4 weeks and the subject has been seizure free for at least 6 months.
5. Presence of SIB classified as automatically maintained, based on functional analysis (described below).

Exclusion Criteria

1. Presence of a known serious medical condition in the child (based on medical history) that would interfere with child ability to participate in the study.
2. Presence of a current serious behavioral problem or psychiatric condition in the child that would require another treatment (e.g., psychotic disorder, major depression) (based on all available information collected at screening). [RATIONALE: children with a serious, untreated psychiatric condition should proceed with treatment for that psychiatric condition.]
3. Prior failed treatment of NAC of at least 1200 mg per day for at least 4 weeks.
4. Presence of unacceptable adverse effects, including but not limited to hypersensitivity reactions, with prior treatment with NAC at any dose.
5. Children with a history of asthma
5. On a psychotropic medication, but regimen is not stable. [RATIONALE: For children on unstable medication regimen it may be difficult to interpret efficacy and/or tolerability of the study treatment. Once stabilized, eligibility could be reconsidered.]

Visit Windows

The visit windows for each assessment visit are:

- FA Screen is -0/+14 days from initial Screen
- Baseline is -0/+14 days from FA screen
- Week 1 is 7 -3/+3 days from Baseline
- Week 2 is 14 -5/+5 days from Baseline
- Week 4 is 28 -7/+7 days from Baseline
- Week 6 is 42 -7/+7 days from Baseline
- Week 9 is 63 is -9/+9 days from Baseline

Aim #2 [Positive Predictive Value]

The screening visit will also include a semi-structured interview to make a **preliminary** determination whether the repetitive behavior is *socially maintained* or *automatically maintained*. Subjects that are classified with a preliminary classification of *automatically maintained* SIB will be invited to participate in the trial and proceed to the baseline visit. We expect to evaluate 18-20 children to randomize 14 eligible and willing subjects.

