Data Verification and Security: The Marcus Informatics and Analytics Core has a sophisticated data management system called DEX. This is a HIPAA-compliant, doubly-encrypted, password-protected database housed and operated at Marcus through a contract with Prometheus Research. All data entered are stored on **secure** servers maintained by Prometheus through a third party called Rackspace. Only pertinent study staff will have access to patient and study-related information. The progress of data collection will be monitored with web-based electronic data form reports, which produces a profile of all forms expected and received for each study subject. Missing-forms reports are available and are electronically accessible by the data manager and the coordinator. We will request reports on missing data, recruitment and compliance every other week. These audits are conducted by the data manager assigned to this study. Outliers and unusual values will be checked for accuracy. Data questions or problems will trigger queries back to the coordinator to assure that all forms are entered and available for analysis. Recurring problems with the data entry system will be resolved via discussion between the data manager, coordinator and PI as necessary. Prometheus contracts with Rackspace to ensure geo-redundant data storage such that in a disaster of the data center that hosts the application, no data will be lost. Nightly system backups are archived for seven days; weekly backups are archived for four weeks; monthly backups are archived for as far back as space will allow. Incremental (binary) backups of all database changes occur every 15 minutes; the write-ahead log monitors incremental changes in the interim and increases backup frequency under heavy usage.

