The statistician, [name], will conduct initial analyses to inspect data for errors, frequency, pattern, time to drop out, and missing data. This will include examination of frequency tables and dot plots for univariate data and scatter plots as needed. Data anomalies and outliers will be identified and addressed in coordination with the PI and data manager. Descriptive statistics will be calculated at baseline and follow-up time points using means and standard deviations, medians and interquartile ranges, or frequencies and percentages as appropriate.

Aim #1: As noted above, the primary aim of this pilot trial is feasibility. We set forth several benchmarks: a) demonstrate capacity to screen 2 subjects/month (in order to average 1.75 randomize subjects/month); b) no more than 15% attrition rate (e.g., no more than 2 of 14 randomized subjects); c) at least 70% compliance with study medication (determined by tablet counts and drug dairies); d) at least 80% collection of essential outcome measures (actual ratings ÷ expected X 100); e) at least 80% of parents will *agree* or *strongly agree* when asked in an anonymous survey that they would recommend the study and the study treatment to other parents of children with ASD and SIB.

Aim #2: 75% positive predictive value (PPV = screen positive and true cases ÷ all positive screens) for our screening method to classify children with automatically maintained self-injurious behavior.

Aim #3: The use of placebo-control in this trial permits blinded assessment. These benchmarks will be examined **within** the NAC group.

- a) Test for significant decline from baseline to Week 9 on the parent-rated Aberrant Behavior Checklist Irritability subscale using a paired t-test.
- b) at least 50% decline (on average) from baseline to Week 9 in the number of SIB events in children treated with NAC when counted by a trained technician who is blind to treatment assignment.

In addition to percent change, we will run ANCOVAs on these outcomes within the NAC group and across treatment groups with baseline values in the model.

c) at least 50% of the subjects randomized to NAC on will be rated *much improved* or *very much improved* on the Improvement scale of the Clinical Global Impression by a clinician blind to treatment assignment.

The other outcomes listed in Table 2 above (Parent Daily Checklist, CYBOCS-ASD) will be performed as exploratory outcomes.

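### Recruitment benchmark (a): the Data Analysis minimum of 2 children screened per month, and the lower end of the 2-3 in Specific Aims, is too low for 1.75 randomised per month if screening runs only over the 8 enrolment months

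*Combined protocol and SAP*

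**What the plan says.** Benchmark (a) of the feasibility aim, which Data Analysis calls the primary aim, appears twice with different values.

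- Data Analysis, Aim #1: "demonstrate capacity to screen 2 subjects/month (in order to average 1.75 randomize subjects/month".
- Specific Aims, Aim #1: "demonstrate capacity to screen 2-3 subjects/month (in order to average 1.75 randomize subjects/month".

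The randomisation target comes from the section Aim #1 [Feasibility]: "Enrollment will occur from Month 2 through Month 9 of the project (average at least 1.75 subjects per month", for fourteen children.

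Two other statements bear on how many screened children reach randomisation.

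- Specific Aims, Aim #2, defines PPV as confirmed cases among "all positive screens, we set a benchmark of 75" per cent. Data Analysis, Aim #2, repeats the 75%. Inclusion criterion 5 requires the functional analysis to classify the self-injury as automatically maintained. The Functional Analysis paragraph excludes children who are reclassified as socially maintained.
- The section Aim #2 [Positive Predictive Value] forecasts the overall yield: "We expect to evaluate 18-20 children to randomize 14 eligible and willing subjects".

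On timing, Visit Windows allows a gap between screening and randomisation: "FA Screen is -0/+14 days from initial Screen" and "Baseline is -0/+14 days from FA screen". No section says in which month screening begins.

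**The concern.** A screening minimum that exists to secure a randomisation rate should be high enough to secure it at the yield that the same plan assumes. A minimum of 2 screened per month leaves room to lose only one child in eight. The PPV benchmark alone allows one in four to be lost at the functional analysis, before any negative interview, other ineligibility or refusal. A team could therefore meet benchmark (a) and the PPV benchmark exactly and still be expected to randomise fewer than 1.75 children per month.

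The two sections also disagree on the pass mark. At 2 per month both would count the benchmark as met, so copying the range into Data Analysis would not remove the problem. What is at stake is whether a feasibility criterion means what it says when the pilot is used to judge readiness for a larger trial.

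**Working it through.** **Inputs.** 14 children randomised; enrolment in Months 2-9; screening minimum 2 per month (Data Analysis) or 2-3 per month (Specific Aims); PPV benchmark 0.75; forecast of 18-20 evaluated for 14 randomised.

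**Step 1: reproduce the target.** Months 2 through 9 are 9 − 2 + 1 = 8 months, and 14 / 8 = 1.75 per month. This matches the plan.

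**Step 2: yield needed at 2 per month.** 1.75 / 2 = 87.5%.

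**Step 3: yield at the PPV benchmark, screening over 8 months.** Randomised per month ≤ screened per month × PPV = 2 × 0.75 = 1.5. Over 8 months that is 16 × 0.75 = 12 of 14. The ratio 1.5 / 1.75 = 0.857 means 14% short. This is an upper bound at 75% PPV, because it takes every screened child to be interview-positive, otherwise eligible and willing. The documents give no separate rate for those losses.

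**Step 4: yield from the plan's forecast, without using PPV.** I read the children evaluated as those attending formal screening. The yield is 14/20 = 70.0% to 14/18 = 77.8%. At 2 per month this gives 2 × 0.700 = 1.40 to 2 × 0.778 = 1.56 per month, which is 20% to 11% short. Spread over 8 months, the forecast itself needs 18/8 = 2.25 to 20/8 = 2.5 children per month.

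**Step 5: rate that is sufficient.** At 75% PPV with no other losses, 1.75 / 0.75 = 2.33 per month.

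| Screened per month | Over 8 months | Randomised per month at 75% PPV, no other losses | Randomised per month at 70% overall yield |
|---|---|---|---|
| 2 | 16 | 1.50 | 1.40 |
| 2.33 | 18.7 | 1.75 | 1.63 |
| 2.5 | 20 | 1.875 | 1.75 |
| 3 | 24 | 2.25 | 2.10 |

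**Step 6: sensitivity to when screening starts.** Suppose screening begins one month before enrolment and runs for 9 months. Then 2 × 9 = 18 children are screened, while the target is still averaged over 8 enrolment months.

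- At 75% PPV: 18 × 0.75 = 13.5 expected, and 13.5 / 8 = 1.69 per enrolment month, 3.6% short.
- At a 14/18 yield: 18 × 14/18 = 14, and 14 / 8 = 1.75, so the gap closes.
- At a 70% yield: 18 × 0.70 = 12.6, and 12.6 / 8 = 1.575, 10% short.

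**The case against.** Four points can fairly be made for the plan.

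1. **The Specific Aims range contains adequate rates.** This stands. At 75% PPV, 2-3 per month gives 1.5 to 2.25 randomised per month. The range also covers the 2.25-2.5 that the plan's own forecast requires. A reader might infer that the whole range falls short; the figures do not support that. Only the part below about 2.33 does, at 75% PPV with no other losses.
2. **Screening may start before enrolment.** This also stands. The two windows allow up to 28 days between Screen and Baseline, so a Month 1 start is plausible. A reader might infer that the monthly shortfall is the same whenever screening starts. It is not, because the target is averaged over enrolment months, and Step 6 shows the gap shrinking or closing. But the documents do not state an early start, and the benchmark should not depend on an unstated one.
3. **75% is a pass mark, not a forecast.** Correct: the Functional Analysis paragraph says reclassification is not expected often. A higher PPV would help, but 2 per month still needs an overall yield of 87.5%, and the plan's own forecast of 70-78% is below that without any appeal to PPV.
4. **A miss would be seen.** This stands too. The 1.75 figure is written into the benchmark and set separately under Aim #1 [Feasibility], and Data Management provides for monitoring: "We will request reports on missing data, recruitment and compliance every other week". A reader might infer that failed recruitment could pass as success. It could not, because the number randomised is directly observed.

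**Conclusion.** The point holds in limited form and is minor. The two statements of benchmark (a) disagree. The Data Analysis figure of 2 per month, with the lower end of the Specific Aims range, is too low on the plan's own yields if screening is confined to Months 2-9. The expected rate is then at most 1.5 per month at 75% PPV (14% short, 12 of 14 children), or 1.40-1.56 at the forecast yield (11-20% short).

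The size rests on three assumptions: screening over the same 8 months as enrolment; for the PPV figure, no losses other than at the functional analysis; and, for the forecast figure, that children evaluated means children formally screened. With a ninth month of screening the gap is 3.6% at 75% PPV and nil at a 14/18 yield. These are expected values. They do not show that recruitment would fail, and no efficacy or safety analysis is affected.

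**What to change.** State one minimum in both places (Specific Aims, Aim #1 a, and Data Analysis, Aim #1 a): capacity to bring at least 2.5 children per month into formal screening, or 20 over the 8 enrolment months. This agrees with the upper end of the plan's forecast. It gives 2.5 × 0.75 = 1.875 randomised per month at the PPV benchmark with no other losses, and 2.5 × 0.70 = 1.75 at the lowest yield that the forecast implies.

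Count children rather than visits, because Table 2 spreads screening over two visits (Screen and FA Screen) and a count of visits could be read as half as many children.

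The cost is one number changed in two places, and a benchmark slightly harder to meet than 2 per month.

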
Aim # 3 [Preliminary Efficacy]

Study outcome measures are listed in Table 2. All outcomes including direct observation of behavior in the laboratory setting, parent ratings of behavior and assessment of overall improvement will be collected blind to treatment assignment. Here we describe the outcome measures that are directly related to preliminary efficacy benchmarks (see Appendix A for detailed description of other outcome measures).

Aberrant Behavior Checklist (ABC) is a 58-item, informant-based scale with five subscales: *I. Irritability* (includes agitation, aggression and self-injurious behaviors, 15 items); *II. Lethargy* (includes social withdrawal, 16 items); *III. Stereotypic Behaviors* (7 items); *IV. Hyperactivity*, 16 items (includes overactivity and impulsiveness); and *V. Inappropriate Speech* (4 items). The ABC has been used as an outcome measure in many studies of children with ASD (RUPP Autism Network, 2002; RUPP Autism Network, 2005; Aman et al., 2009; Hardan et al., 2012; Bearss et al., 2015). In this proposed study, the parent-rated Irritability subscale will be of particular interest because it includes items on SIB. We will also be interested in the Stereotypy subscale.

Direct observation of the frequency and severity of SIB will also be collected at baseline and endpoint at the conclusion (but separate from) of the functional analysis. Operational definitions will be created for each child based on the parental description of the SIB. For example, if the child engages in hand-to-head hitting, the operational definition may be anytime the child's hand comes in contact with the head from a distance of 6-inches or greater. Similarly, for a child who engages in hand-biting the definition may be when the child's teeth make contact with the hand. Frequency data will be collected for any discrete behavior (such as head banging) and duration data will be collected for behaviors that

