may occur for longer periods of time (such as hand biting). Real-time counts of SIB will be tallied by a trained rater (blind to treatment condition) during a set of structured, 10-minute conditions that will include routine demand, restricted access to tangible items, restricted access to attention, free play with free access to parent-identified preferred items, and when the child is left alone in an austere environment. The rater will also complete a 4-point severity rating scale of SIB (0=none, 1=mild, 2=moderate, 3=severe) for each condition. A skin check is performed following sessions with moderate levels of self-injurious behavior, which will document marks likely caused by the behavior observed in a session. The child's visible body parts (i.e., arms, face) and any targeted body parts (e.g., back, scalp) will be assessed. Data collectors will denote the severity rating based off of the skin checks. Per minute counts of SIB across the entire length of the observational period as well as per minute counts in different conditions (routine demands, restricted access to tangible items, restricted access to attention, free play, and alone in austere environment). An average of the 10-minute severity ratings will also be calculated at baseline and endpoint. Change in counts and the average severity score within the NAC group (paired t test) and across treatment groups (ANCOVA) will be used to evaluate preliminary efficacy. Counts and severity during the alone condition (automatically maintained SIB) will be analyzed separately.

Parent Target Problems At baseline, parents will be asked to nominate the two most important problems for the child. Through brief discussion, the frequency (for episodic behaviors) or constancy (for problems such as impulsiveness reflecting more enduring patterns), intensity and impact of the behavior on the family are established. Responses from this systematic inquiry are documented in a brief narrative. The narrative will be reviewed at Weeks 2, 6 and 9 and a new narrative documented. This review will assist with the scoring of the CGI-I in real time ([name] et al., 2015).

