Improvement item on the Clinical Global Impression scale (CGI-I) The CGI-I is a 7-point scale designed to measure overall improvement from baseline ([name] et al., 2015). Scores range from 1 (Very Much Improved) to 4 (Unchanged) to 7 (Very Much Worse). The CGI-I will be used to assess overall response to treatment. By convention, scores of Much Improved or Very Much Improved are used to define *positive response*; all other scores are classified as a *negative response*. Using available information (ABC scales, Parent Target Problems, Parent Daily Rating), the CGI-I will be rated by a blinded independent evaluator ([name]) trained by [name].

Aim #4 [Safety and Tolerance]

A blood sample for routine lab tests (CBC, BUN, creatinine, liver function panel) will be collected at screening and at endpoint. These lab results will be reviewed by [name] (Pediatric Nurse Practitioner) with consultation from Drs. [name] and [name] as needed. Clinically important findings will be shared with the family.

Adverse Events At each visit the treating clinician will ask specific queries about major body systems, activity level, sleep, appetite, and general health. The assessment will be guided by the Adverse Events Review. This measure will be conducted at baseline so that current health complaints are known and documented. New events, whether presumed related to treatment or not, are classified as an adverse event and rated as Mild, Moderate or Severe (See Appendix B for definitions).

Aim #5 [Biomarkers and Mechanism of Action]

In addition to the blood drawn for safety monitoring, we collect an additional tube (2 cc, lavender top) of whole blood to examine redox couples and amino acid neuromediator levels before and after NAC treatment. Samples will be centrifuged twice to obtain platelet-free plasma. These samples will be analyzed in [name] lab using ultra-sensitive, quantitative mass spectrometry methods (Tirouvanziam et al., 2006; Tirouvanziam et al., 2012; Hardan et al., 2012; Conrad et al., 2015). NAC has been shown to affect cysteine/cystine and glutathione/glutathione disulfide (GSH/GSSG) redox couples in blood, as well as levels of glutamate, glutamine and possibly, GABA. Measurement of these indices may inform the possible mechanisms of action of oral NAC (e.g., rebalancing key redox metabolites and/or excitatory/inhibitory amino acids) that may be relevant in the treatment of SIB in children with ASD.

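### Is the 80% outcome-collection benchmark, Aim #1 (d), too loosely defined to be judged?

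*Combined protocol and SAP*

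**What the plan says.** Benchmark (d) appears in Specific Aims, Aim #1, and again in Data Analysis, Aim #1: "at least 80% collection of essential outcome measures", with actual ratings divided by expected ratings, times 100. Neither place lists the essential measures or visits.

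Other sections bear on it:

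- **Measures.** The Approach section for Aim #3 opens its list with "Here we describe the outcome measures that are directly related to preliminary efficacy benchmarks" and sends the remaining outcomes to Appendix A. It then covers the ABC, direct observation, Parent Target Problems and the CGI-I. The three Aim #3 benchmarks in Data Analysis use the ABC Irritability subscale, the count of self-injury events and the CGI-I. The same section calls other outcomes exploratory.
- **Visits.** Table 2.0 marks the ABC at screening, baseline and Weeks 4 and 9; the CGI-I at baseline and Weeks 4 and 9; and the "Direct Observation Session" at baseline and Week 9.
- **Unit.** Data Verification and Security describes a report of forms expected and received for each child.
- **Attrition.** Benchmark (b) tolerates two losses among 14 randomized children. Families who stop treatment are asked to keep attending, or to come to an early termination visit.

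Benchmark (e) asks for 80% of parents agreeing "that they would recommend the study and the study treatment to other parents of children with ASD and SIB". The Appendix A outline of the satisfaction form, which is still to be developed, mentions recommending the study only.

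**The concern.** Feasibility is the primary aim, and (d) is the only benchmark on whether outcomes were collected. A threshold without a stated numerator and denominator invites a choice made after the data are seen, and the team reviews the data-collection rate at least monthly.

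The surrounding text also has loose ends:

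- The Aim #3 section describes four measures, but the benchmarks use three.
- Table 2.0 marks a baseline CGI-I, although "The CGI-I is a 7-point scale designed to measure overall improvement from baseline".
- For "Parent Target Problem", Table 2.0 marks screening, baseline, Week 4 and Week 9, while the text sets it up at baseline and then says "The narrative will be reviewed at Weeks 2, 6 and 9 and a new narrative documented".
- An observation session has five conditions, and "The rater will also complete a 4-point severity rating scale of SIB (0=none, 1=mild, 2=moderate, 3=severe) for each condition", so a session might be counted as one rating or five.

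If these choices moved the result across 80% under realistic losses, the pilot could report success or failure on collection from identical data.

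**Working it through.** **Reproducing the plan's figures.** The 80% is a chosen cut-off, so there is no derived figure to reproduce. The neighbouring arithmetic holds: 2/14 = 14.3%, within the 15% of benchmark (b), and 8 months × 1.75 = 14 children.

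**Inputs.** There are 14 randomized children. From Table 2.0, the forms per child are ABC 4, CGI-I 3 and direct observation 2. The denominator is all randomized children, which is the stricter choice.

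**Assumed losses (not document figures).** Two children leave after baseline and supply nothing further, and three of the other 12 miss the Week 9 observation. This is harsher than the plan expects, because it gives no credit for continued or early termination assessments.

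**Formula.** Collected = 14 × forms per child − 2 × forms lost per dropout − 3 × ratings lost per missed session.

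| Reading | Expected | Needed for 80% | Collected | Result |
|---|---|---|---|---|
| Three measures, all Table 2.0 visits | 9 × 14 = 126 | 101 | 126 − 10 − 3 = 113 | 89.7%, pass |
| Same, without screening ABC and baseline CGI-I | 7 × 14 = 98 | 79 | 98 − 10 − 3 = 85 | 86.7%, pass |
| Only what Aim #3 uses (ABC and observation at baseline and Week 9, CGI-I at Week 9) | 5 × 14 = 70 | 56 | 70 − 6 − 3 = 61 | 87.1%, pass |
| All visits, each observation condition counted | (4 + 3 + 2 × 5) × 14 = 238 | 191 | 238 − 18 − 15 = 205 | 86.1%, pass |
| Three measures, Week 9 only | 3 × 14 = 42 | 34 | 42 − 6 − 3 = 33 | 78.6%, fail |
| Observation at Week 9 alone | 14 | 12 | 14 − 2 − 3 = 9 | 64.3%, fail |

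**Two dropouts and no other loss.** The six readings give 116/126 = 92.1%, 88/98 = 89.8%, 64/70 = 91.4%, 220/238 = 92.4%, 36/42 = 85.7% and 12/14 = 85.7%. All pass.

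**Room before failure.** With two dropouts, the number of the other 12 who can miss the Week 9 observation while (d) still passes is 12, 9, 8, 5, 2 and 0, in table order.

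**Which readings the text supports.**

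- The formula is a single ratio over measures in the plural, which points to pooling. A count of one measure at one visit does not fit it.
- Nothing in (d) limits the expected ratings to Week 9.
- The system counts forms, and Table 2.0 gives the observation session one row, so one session is naturally one unit. The fourth row is strained, and it passes anyway.
- Parent Target Problems is a narrative that helps the evaluator score the CGI-I, and no Aim #3 benchmark is computed from it. Its schedule mismatch leaves baseline and Week 9 unaffected and does not enter any row above.
- A baseline CGI-I is redundant by the scale's definition. Dropping it together with the screening ABC takes the first row to the second, and both pass.

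**Benchmark (e).** If 12 of 14 families answered and 10 agreed (assumed), the result would be 10/12 = 83.3% or 10/14 = 71.4%. The benchmark is worded in terms of parents who were asked, so the natural base is those surveyed.

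**The case for a change.** The best case for a change is that a primary-aim criterion should be fixed before anyone sees the data, and that a single sentence would fix it. The split can also come with milder losses: two dropouts and one further missed Week 9 observation give 11/14 = 78.6% for that measure at that visit, against 87/98 = 88.8% pooled. In the extreme the pooled readings themselves part. With two dropouts and no Week 9 observation in the other 12, the widest count gives 104/126 = 82.5% while the second gives 76/98 = 77.6%.

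It stands that the definition is missing and that a benchmark pooled over visits can hide the loss of one measure at one visit. It does not follow that the plan must change. The milder split needs a single-measure reading, or one requiring each child to have a complete Week 9 set. The extreme split needs the loss of every Week 9 observation, which would leave the Aim #3 benchmark on self-injury counts without data and would show in the missing-forms reports. A tighter rule does not remove the weakness either: the five-form rule reaches 56/70 = 80.0% with all 14 Week 9 observations missing. What exposes such a loss is the number of children with each measure at Week 9, and the planned descriptive statistics at follow-up already provide for that.

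On (e), the missing treatment question and the unstated order of the survey and the Week 9 unblinding are real omissions. They concern a form described only in outline, and the benchmark itself already says what that form must ask.

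**Conclusion.** This is a gap that analysts will fill sensibly, and no change to the plan follows. The formula, the form-level tracking and the Aim #3 benchmarks lead to a pooled count of the ABC, direct observation and CGI-I. The reasonable versions of that count agree: all pass at 86.1% to 89.7% in the assumed adverse case, and at 89.8% or more with two dropouts alone. The result turns only on a Week 9-only or single-measure reading that the wording does not suggest, or on losses large enough to be plain without the benchmark. Benchmark (d) is descriptive, with no test attached and no numerical rule tying it to the decision on a larger trial.

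The conclusion rests on Table 2.0 as it reads in the extracted text and on assumed patterns of loss, since the documents give none. The differing Parent Target Problems visits are a clerical slip to reconcile when the document is next revised. They do not affect (d) as counted here, or the Week 9 data that Aim #3 uses.
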